**Research Aims:**

1. **Research Questions(s)** (1) Does spatial orientation of a novice in relation to a mannequin (supine vs upright) impact on the development of fiberoptic intubation skills (2) Is it necessary to teach both orientations or is the supine view transferable to the upright position. (3) Which method demonstrates longer skill retention.
  
2. **Hypotheses** (1) Both orientations must be practiced. (2) The upright skill is harder to learn but is retained for longer.

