**Significance:**

Novices better prepared in the skills of manipulating a fiberoptic will take less time and have a higher success rate of fiberoptic intubation. These skills must be taught for both spatial orientations and practiced to be retained

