**Statistical Methods:**

60 medical students will be consented to allow for dropout. Based on a repeated – measures design with one between-factor design (supine vs upright) and one within factor (repetitions), four groups with 10 subjects each with each subject measured 10 times, achieves 87% power to measure a difference in time to visualize the carina using a Geisser -Greenhouse Corrected F-test at a 5% significance level assuming an effect size of 0.7. Groups A ,B,C,D will be compared. The two outcome measures global rating scale (GRS) and examiner check list (ECL) scores will be analyzed using a two-way, mixed design ANOVA. Categorical data such as success failure will be analyzed by Fisher exact test. Time to intubation will be analyzed using the MannWhitney U test.

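### Question 2 allows the answer that supine training transfers to upright, but the plan has only difference tests, so that answer could come only from a non-significant result

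*Combined protocol and SAP*

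**What the plan says.** Under Research Aims, the second question offers two answers: "Is it necessary to teach both orientations or is the supine view transferable to the upright position". The matching hypothesis is "Both orientations must be practiced", and the Significance section says the same: "These skills must be taught for both spatial orientations and practiced to be retained".

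Phase one describes four groups. Groups B and C are both tested on the upright mannequin first; B has practised upright on the app and C supine. Groups A and D are tested supine first and upright second.

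Statistical Methods gives one power statement: "four groups with 10 subjects each with each subject measured 10 times, achieves 87% power". Its aim is "to measure a difference in time to visualize the carina", with a Geisser-Greenhouse "Corrected F-test at a 5% significance level assuming an effect size of 0.7". The other listed analyses are a mixed-design ANOVA for the two rating scores, Fisher's exact test for success or failure, and the Mann-Whitney test for time to intubation. The only statement on which groups are compared is "Groups A ,B,C,D will be compared".

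**The concern.** Every listed analysis tests whether groups differ. Such a test can support the answer that training is orientation-specific. It cannot by itself support the answer that supine training carries over to upright, because a non-significant result fits both true transfer and an imprecise study. The plan gives no estimate with an interval, no margin for an acceptable deficit, and no named contrast for this question, so nothing separates the two explanations.

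The background motivates the study with difficult-airway patients who present sitting up. If a null result were read as transfer, upright training could be judged unnecessary because the study lacked precision.

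**Working it through.** **Which contrast.** Upright performance without earlier mannequin attempts is available only in B and C, since A and D reach the upright mannequin after a supine test. C v B on the first-tested block is therefore the direct transfer comparison. It has 10 v 10 in the power statement, and 60/4 = 15 v 15 if all 60 consented students complete and are split equally.

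**The plan's own figure.** The 87% cannot be uniquely reproduced, because the type of effect size and the correlation between repeats are not given. For a between-group effect on the mean of m = 10 repeats, take a noncentral F with λ = N·f²·m / (1 + (m − 1)ρ).
- Four groups, N = 40, f = 0.7: even at ρ = 1, λ = 40 × 0.49 = 19.6 and power is 95.4%. It is higher for smaller ρ, so 87% is not matched.
- 0.7 as a standardised difference (f = 0.35), two pooled groups of 20: 87% at ρ ≈ 0.43.
- Four groups with f = 0.35: 87% at ρ ≈ 0.27.

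None of these is the C v B contrast, so the implied 13% miss rate does not apply to it.

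**Miss rate for C v B.** Two-sample t-test, two-sided 5%, noncentrality (d/s)·√(n/2). Here s = 1 for one measurement, and s = √((1 + 9ρ)/10) for the mean of 10 repeats, in units of the single-measurement SD. This gives s = 0.608, 0.742 and 0.854 at ρ = 0.3, 0.5 and 0.7. Three things are assumed: these values of ρ, that 0.7 is a standardised difference, and that all 10 repeats fall in the upright block (the plan does not say how they divide between orientations).

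| d = 0.7 | 10 v 10: power / missed | 15 v 15: power / missed |
|---|---|---|
| One measurement | 31.7% / 68% | 45.7% / 54% |
| 10 repeats, ρ = 0.3 | 68.2% / 32% | 86.0% / 14% |
| 10 repeats, ρ = 0.5 | 51.5% / 49% | 70.4% / 30% |
| 10 repeats, ρ = 0.7 | 41.1% / 59% | 58.2% / 42% |

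Example: n = 10, ρ = 0.5 gives noncentrality (0.7/0.742) × √5 = 2.11 on 18 df, and power 51.5%.

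If 0.7 is Cohen's f, then d = 2 × 0.7 = 1.4 for two groups. At 10 v 10 the miss rate is 16% on one measurement and 2% on 10 repeats at ρ = 0.5.

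**Precision.** The 95% half-width is t(0.975, 2n − 2)·s·√(2/n). This does not depend on how 0.7 is defined.
- 10 v 10: 2.101 × √0.2 = 0.94 SD on one measurement; 0.57, 0.70 and 0.80 SD on 10 repeats at ρ = 0.3, 0.5 and 0.7.
- 15 v 15: 0.75 SD on one measurement; 0.45, 0.56 and 0.64 SD on 10 repeats.

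At 10 v 10 with ρ = 0.5, an observed difference of exactly zero rules out only deficits above about 0.70 SD.

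**The case against.** The strongest reply is that the stated hypothesis is one of difference, that the investigators expect a difference, and that difference tests suit it. That stands. The gap affects only the other answer that the question itself allows. It is also true that nowhere do the documents say a null result will be read as transfer, or that upright training would then be dropped. That harm is an inference from the plan's silence.

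Three stronger readings are tempting, and the documents do not support them.
- *A null result is likely whenever transfer fails.* The 68% applies to one measurement per student, while the powered analysis uses 10. On repeats the miss rate runs from below to above one half, depending on an unstated correlation, and it is small if 0.7 is Cohen's f.
- *A null result at 10 v 10 can never exclude a 0.7 SD deficit.* It can. With a half-width of 0.94, an observed difference of −0.3 SD gives −1.24 to 0.64, which is non-significant yet excludes 0.7.
- *No group practises both orientations, so the need for both cannot be supported.* No group is initially taught both on the app, but every student is tested on the mannequin in both. The design also examines transfer in each direction (C v B upright, D v A supine), and deficits both ways would be relevant evidence. This is a secondary matter of wording.

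Pooling supine-taught against upright-taught students (20 v 20) gives 83% power at d = 0.7 and ρ = 0.5. That helps, but it mixes in students who had already been tested supine on the mannequin before their upright test.

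**Conclusion.** The concern holds in a limited form. The plan has no valid route to one of the two answers to Question 2, because it names no contrast, interval or margin for transfer. How often a real deficit would be missed is not fixed by the documents. At 10 v 10 and a 0.7 SD deficit it is 68% on one measurement and 32% to 59% on 10 repeats; at 15 v 15 with 10 repeats it is 14% to 42%. Under the Cohen's f reading it is 16% or less at 10 v 10. These figures rest on assumed correlations and on a reading of 0.7 that the plan does not supply. The interval widths need no reading of 0.7. They show that a difference near zero may still leave a material deficit possible.

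**What to change.** In Statistical Methods, name C v B in upright time to carina on the first-tested block, using all repeats, as the transfer analysis. Report the difference (C minus B, positive meaning slower after supine teaching) with its 95% CI. Treat the pooled comparison by teaching orientation as supportive. State that a non-significant p-value will not be reported as transfer.

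Fix and justify a one-sided margin before data collection, and use four exclusive conclusions:
- Upper limit below the margin, lower limit not above zero: transfer.
- Upper limit below the margin, lower limit above zero: a deficit smaller than the margin.
- Lower limit above zero, upper limit not below the margin: a deficit.
- Anything else: not established.

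The rule is one-sided so that faster times in supine-taught students are not labelled a failure of transfer.

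The cost is plan wording and one interval from data already to be collected. The sponsor must choose the margin, and a finding of not established is realistic. With no true difference and ρ = 0.5, the chance that the upper limit falls below an assumed margin of 0.7 SD is 51.5% at 10 v 10 and 70% at 15 v 15. For an assumed margin of 0.5 SD it is 30% and 43%.

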**Phase one :**

Sixty medical students, novices in fiberoptic intubation use will be recruited and randomly assigned into one of two groups:

**Group A** (supine-supine) will first practice fiberoptic intubation with the iLarynx oriented in the supine position. Learning curves, global rating scale and checklist will then be obtained by a blinded examiner with the medical student using a real fiberoptic on a mannequin oriented in the supine, then upright position. At the end of one week, the same medical student will then perform the intubation with the mannequin in both positions.

**Group B** (upright-upright) will first practice fiberoptic intubation with the iLarynx oriented in the upright position. Learning curves, global assessment score and checklist will then be obtained by a blinded examiner with the medical student using a real fiberoptic on a mannequin oriented in the upright then supine position. At the end of one week, the same medical student will then perform the intubation with the mannequin in both positions.

**Group C** (supine –upright) will first practice fiberoptic intubation with the iLarynx oriented in the supine position. Learning curves, global assessment score and checklist will then be obtained by a blinded examiner with the medical student using a real fiberoptic on a mannequin oriented in the upright then supine position. At the end of one week, The same medical student will then perform the intubation with the mannequin in both positions.

**Group D** ( upright – supine) will first practice fiberoptic intubation with the iLarynx oriented in the upright position. Learning curves, global assessment score and checklist will then be obtained by a blinded examiner with the medical student using a real fiberoptic on a mannequin oriented in the supine, then upright position. At the

end of one week, the same medical student will then perform the intubation with the mannequin in both positions.

	teachin g		testing	testing		week	testing	testing
A	supine		supine	upright	i/droid	upright	supine	
B	upright		upright	supine	i/droid	supine	upright	
C	supine		upright	supine	i/droid	upright	supine	
D	upright		supine	upright	i/droid	upright	supine	

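### Phase one can test whether iLarynx practice is orientation-specific, but it cannot measure absolute transfer or directly test whether both orientations must be practised

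*Combined protocol and SAP*

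**What the plan says.** Research Aims asks, as its second question, "Is it necessary to teach both orientations or is the supine view transferable to the upright position". Hypothesis 1 answers that "Both orientations must be practiced", and the Significance section repeats this as a conclusion: "These skills must be taught for both spatial orientations and practiced to be retained".

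Phase one assigns app practice and mannequin order as follows.

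- Groups A and C: each "will first practice fiberoptic intubation with the iLarynx oriented in the supine position".
- Groups B and D: each "will first practice fiberoptic intubation with the iLarynx oriented in the upright position".
- Groups A and D are then examined "using a real fiberoptic on a mannequin oriented in the supine, then upright position".
- Groups B and C are examined "using a real fiberoptic on a mannequin oriented in the upright then supine position".

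The table at the end of Phase one agrees on these points. All students are retested in both positions at one week. Phase two randomises students to a week of daily app practice or to none; it does not say which orientation is practised. Statistical Methods says only that the four groups will be compared. It names no contrast for question 2 and gives no rule for reading a result of no difference.

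**The concern.** The hypothesis is about practising both orientations, but app practice before the first test is always in one. Two comparators that the wording calls for are absent: a group that practises both on the app, and a group that goes to the mannequin untrained.

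The practical conclusion of the trial is whether to teach one orientation or two. Question 2 offers transferability as the alternative to teaching both, so a finding of no difference invites that label, although an app without effect would give the same data. A finding of a difference invites the statement that both must be taught, although no group was taught both on the app.

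**Working it through.** **Inputs.** All come from Phase one. Write b_S and b_U for the mean performance of an untrained novice at the supine and upright mannequin, and g(x→y) for the gain that app practice in orientation x gives at test position y. Higher is better.

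| Group | App practice | First test | Expected first-test mean |
|---|---|---|---|
| A | supine | supine | b_S + g(S→S) |
| D | upright | supine | b_S + g(U→S) |
| B | upright | upright | b_U + g(U→U) |
| C | supine | upright | b_U + g(S→U) |

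Groups practising both on the app: 0 of 4. Groups untrained at the first test: 0 of 4.

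**What can be estimated.**

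- B − C = g(U→U) − g(S→U), the matched-minus-mismatched difference at upright.
- A − D = g(S→S) − g(U→S), the same difference at supine.

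**What cannot.** Add any constant k to b_U and subtract k from both g(U→U) and g(S→U): the expected means of B and C do not change. The transfer gain g(S→U) is therefore not identified, and neither is the matched gain g(U→U). The same holds at supine. The gain from practising both appears in none of the four means, so both-minus-one is not identified either. A matrix-rank check of this model agrees. With the four groups only B − C and A − D are estimable. An untrained group would make the absolute gains estimable, and adding a both-orientation group as well would make both-minus-one estimable. More students in the existing groups would change none of this.

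**Reading each outcome at the first test.**

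- B better than C: upright practice is worth more at upright than supine practice is. At least one of the two gains is not zero, so app practice had some effect. Partial transfer, no transfer and interference from supine practice all remain possible.
- B equal to C and A equal to D: g(S→U) = g(U→U) and g(U→S) = g(S→S). Full transfer fits. So does every gain being zero.
- B equal to C but A better than D: the app had an effect at supine, but the ambiguity at upright remains, and upright is the position question 2 asks about.

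**Second-position tests.** Before its upright test, D has had upright app and supine mannequin practice, while A has had supine app and supine mannequin practice. C against B at supine is the mirror image. These contrasts compare mixed with single-orientation exposure, but they combine app and real-scope practice. No group has matched practice on both media before its second test, so the comparison of both with matched-only is still missing.

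**How likely a null is.** The plan states 87% power for four groups of 10 measured 10 times at an effect size of 0.7. That figure cannot be determined from its inputs, because neither the scale of the effect size nor the within-subject correlation is given. A between-group F-test on one measurement gives 95.4% if 0.7 is Cohen's f and 39.2% if it is d (f = 0.35). For one contrast of two equal groups f = d/2, so the readings are d = 1.4 and d = 0.7. A two-sided 5% t-test on one measurement then has this power:

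| Per group | d = 0.7 | d = 1.4 |
|---|---|---|
| 10 | 32% | 84% |
| 15 (60/4, no dropout) | 46% | 96% |

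Averaging repeats would change these figures. They show only that a null is a live possibility under one of the two readings. The identification argument does not depend on them.

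**The case against.** The strongest reply is that the design does bear on question 2. B against C and A against D are randomised contrasts, and question 2 is put as an either/or. If B beats C, supine practice does not fully substitute for upright practice. That supports hypothesis 1 indirectly and shows that the app did something. This stands. A reader might infer that the trial cannot support hypothesis 1 at all, or that every result is ambiguous between transfer and no effect; the documents do not support either reading. The ambiguity belongs to a null result.

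A reader might also infer that matched against mismatched app practice is the only information available, or that mixed-orientation exposure is never observed. That too goes too far. Hypothesis 1 is not limited to the app, and the second-position tests give randomised contrasts with mixed exposure. A's second-position upright test against C's first-position upright test also shows what supine mannequin work adds at upright. But this is mixed with general familiarity with the scope, and the plan names none of these contrasts. They are supportive only. By one week every student has handled the scope in both positions, so the retests do not restore a single-orientation comparator.

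Two further mitigations are partial. Phase two has a no-practice arm, so it would be wrong to say that the trial has no unpractised group of any kind. That arm is formed after app training and mannequin testing, so it addresses retention and is not an untrained control. The Background cites the team's earlier study as showing that iLarynx helps skill acquisition. This makes an inert app less likely, but the evidence is external and non-concurrent, and the protocol does not say that it covered both orientations.

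Finally, the plan nowhere commits to reading a null as transfer, and Significance is a rationale section. That is fair: the risk is of a conclusion the plan leaves open, not one it prescribes.

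**Conclusion.** The point holds in this form. Phase one can test orientation-specificity through two randomised first-position contrasts. It cannot measure the absolute transfer of app practice, and it cannot directly compare practising both orientations with matched single-orientation practice at equal practice. A positive result supports hypothesis 1 indirectly; a null cannot distinguish full transfer from no app effect.

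The size is structural: 0 of 4 groups practise both on the app, 0 of 4 are untrained at the first test, and no sample size repairs this. The conclusion rests on reading Phase one as written, with app practice in one orientation only before the first test. The first attempts at the first position are the cleanest data, since each repeat is itself real-scope practice in the tested position. The plan should be changed on this point, but the change is one of wording and named contrasts.

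**What to change.** 1. In Research Aims, restate hypothesis 1, and in Significance the matching claim, as: practice matched to the test orientation gives better first-position performance than mismatched practice. The retention part of the Significance sentence is a separate matter and is not affected.
2. In Statistical Methods, replace the general comparison of the four groups with B against C (upright) and A against D (supine), both at the first mannequin position, as the named contrasts for question 2. Describe D against A at upright and C against B at supine, in second position, as supportive only.
3. State that a null will be reported as no orientation-specific benefit shown, not as transfer, and that no direct claim will be made that teaching both is better than teaching one.

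The cost is a narrower conclusion; no students or procedures are added.

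I would not ask for a fifth, both-orientation group within the planned number ("60 medical students will be consented to allow for dropout"). Five groups of 12 make 60, but the reserve above 10 per group falls from 5 (20/60 = 33%) to 2 (2/12 = 17%). If the new group's first position is randomised, each contrast has about 6 against 12, with power of 26% at d = 0.7 and 75% at d = 1.4 (two-sided 5% t-test, one measurement). Splitting the same app time halves practice per orientation, and with no untrained group the ambiguity of a null would remain.

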**Research significance:**

**Background:** With the introduction of the Glidescope in the 2000's, fiberoptic skills are not practiced as frequently as in the past. We are frequently challenged with difficult airways in both the operating room and ICU. Patients with adult epiglottitis, upper airway tumors, severe OSA, CHF present sitting up frequently drooling because the added weight of the lung helps "tent open" the airway. These patients are not Glidescope candidates. Currently, a mannequin consisting of a rubber model mold of the airway is the only cost effective training tool that can be used by the novice to develop the necessary hand-eye co-ordination skills needed for successful fiberoptic intubation. Virtual reality systems that incorporate a real bronchoscope handle interfaced with a computer and monitor could represent an ideal teaching tool, but are expensive. The Orsim trainer can provide fibroptic training in both the supine and upright positions, but costs \$18,000. We developed a simple, inexpensive application, *iLarynx*, for the iPhone or iPad that gives the novice the ability to practice fiberoptic intubation without going to a designated skills lab. A recent MEDLINE review of the literature concludes that training on nonspecific video

games improves endoscopic performance of novices when tested on simulators. The iLarynx is available for free at the iphone app store . At present, over 75,000 copies were distributed worldwide. Our study, that the iLarynx helps improve acquisition of the skills needed for fiberoptic intubation, was accepted for publication in the journal Anaesthesia.

**Significance:**

Novices better prepared in the skills of manipulating a fiberoptic will take less time and have a higher success rate of fiberoptic intubation. These skills must be taught for both spatial orientations and practiced to be retained

**Investigational Plan:**

Following IRB approval, written consent to participate in the study will be obtained from medical students

**Phase one :**

Sixty medical students, novices in fiberoptic intubation use will be recruited and randomly assigned into one of two groups:

**Group A** (supine-supine) will first practice fiberoptic intubation with the iLarynx oriented in the supine position. Learning curves, global rating scale and checklist will then be obtained by a blinded examiner with the medical student using a real fiberoptic on a mannequin oriented in the supine, then upright position. At the end of one week, the same medical student will then perform the intubation with the mannequin in both positions.

**Group B** (upright-upright) will first practice fiberoptic intubation with the iLarynx oriented in the upright position. Learning curves, global assessment score and checklist will then be obtained by a blinded examiner with the medical student using a real fiberoptic on a mannequin oriented in the upright then supine position. At the end of one week, the same medical student will then perform the intubation with the mannequin in both positions.

**Group C** (supine –upright) will first practice fiberoptic intubation with the iLarynx oriented in the supine position. Learning curves, global assessment score and checklist will then be obtained by a blinded examiner with the medical student using a real fiberoptic on a mannequin oriented in the upright then supine position. At the end of one week, The same medical student will then perform the intubation with the mannequin in both positions.

**Group D** ( upright – supine) will first practice fiberoptic intubation with the iLarynx oriented in the upright position. Learning curves, global assessment score and checklist will then be obtained by a blinded examiner with the medical student using a real fiberoptic on a mannequin oriented in the supine, then upright position. At the

end of one week, the same medical student will then perform the intubation with the mannequin in both positions.

	teachin g		testing	testing		week	testing	testing
A	supine		supine	upright	i/droid	upright	supine	
B	upright		upright	supine	i/droid	supine	upright	
C	supine		upright	supine	i/droid	upright	supine	
D	upright		supine	upright	i/droid	upright	supine	

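### All four groups train on the mannequin in both orientations before the retention week, so the one-week A-D comparison does not estimate retention after single-orientation training, and no within-student contrast is defined for Hypothesis 2

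*Combined protocol and SAP*

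**What the plan says.** Research Aims, Question 3, asks "Which method demonstrates longer skill retention". Hypothesis 2 states "The upright skill is harder to learn but is retained for longer".

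Under Phase one, the app teaching uses one orientation. Groups A and C "will first practice fiberoptic intubation with the iLarynx oriented in the supine position"; Groups B and D "will first practice fiberoptic intubation with the iLarynx oriented in the upright position". A mannequin session follows: "Learning curves, global rating scale and checklist will then be obtained by a blinded examiner" (the wording for Group A; the other groups' text is nearly the same). A and D do this "using a real fiberoptic on a mannequin oriented in the supine, then upright position". B and C do it "using a real fiberoptic on a mannequin oriented in the upright then supine position". After one week every group is retested in both positions.

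The Phase one table gives a fixed retest order: upright first in A, C and D, supine first in B. Phase two says the retest order is random. It also randomises students, 20 per group, to daily app practice or no practice during the week, without stating the orientation practised.

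Statistical Methods takes supine versus upright as the between-subject factor and repetitions as the within-subject factor, for "four groups with 10 subjects each with each subject measured 10 times". It says that A-D will be compared, but does not say at which time point or for which research question.

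**The concern.** Question 3 reads most naturally as asking whether a skill learned supine or one learned upright lasts longer. Repeated attempts with a real scope on a mannequin are hands-on practice, and a learning curve presupposes improvement across attempts. Every student has had that practice in both positions before the week begins. The groups then differ only in the app view used beforehand and in the order of the two mannequin blocks.

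Two things are at stake. First, a small one-week difference among A-D could be reported as showing that training orientation does not matter for retention, when no group was trained in one orientation only. Second, Hypothesis 2 compares the upright skill with the supine skill. That comparison lies within each student, and the written analysis contains no term for it.

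**Working it through.** **The plan's own figure.** The only figure is 87% power at effect size 0.7 and 5% significance. It cannot be confirmed, because the type of effect size, the SD and the within-student correlation are not given. Noncentral F calculations give:

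- f = 0.7, four groups of 10: noncentrality 0.49 × 40 = 19.6 on 3 and 36 df, power 95.4%.
- f = 0.7, 10 v 10: 0.49 × 20 = 9.8 on 1 and 18 df, power 84.1%.
- d = 0.7, 20 v 20, one measurement: 0.49 × 20/2 = 4.9 on 1 and 38 df, power 57.8%.
- d = 0.7, 20 v 20, mean of 10 measurements with an assumed correlation of 0.43: variance factor (1 + 9 × 0.43)/10 = 0.487, noncentrality 4.9/0.487 = 10.06, power 87.1%.

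The point does not depend on this figure.

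**Exposure before and at the retest** (Phase one text and table):

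| Group | App | Mannequin before the week | Retest order in table |
|---|---|---|---|
| A | supine | supine, upright | upright, supine |
| B | upright | upright, supine | supine, upright |
| C | supine | upright, supine | upright, supine |
| D | upright | supine, upright | upright, supine |

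Groups with both mannequin positions before the week: 4 of 4. Groups with one only: 0 of 4. If the 10 measurements are per position, each student has 10 supine and 10 upright attempts; if they are a total split evenly, 5 and 5. The document does not say which, and the count of groups is the same either way.

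**What A-D at one week can estimate.** The layout is a 2×2: app orientation (A+C v B+D) by first mannequin orientation (A+D v B+C). Both contrasts are randomised, and both are conditional on later exposure to both positions.

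**What dilution could cost (illustration only).** Take the 20 v 20 case above (d = 0.7, assumed correlation 0.43). If shared exposure left 75%, 50% or 25% of the effect, power would fall from 87% to 64%, 34% or 12%. The documents do not say how much would remain.

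**The within-student contrast and retest order.** For each student, let D be the upright change minus the supine change over the week. Let θ be its true mean and w the advantage of being tested second at the retest, with 10 students per group.

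- Pre-week order is balanced: 20 supine first (A, D), 20 upright first (B, C).
- Under the table's retest order, 30 students are upright first, with expected D = θ − w, and 10 are supine first, with expected D = θ + w. The mean is θ − w(30 − 10)/40 = θ − 0.5w.
- Adjusting for pre-week and retest order removes this bias if the order effects are additive. The estimate of θ becomes half the sum of the A+D mean and the B mean, so Group C contributes nothing. Its variance is σ²(1/20 + 1/10)/4 = 0.0375σ², against σ²/40 = 0.025σ² for a balanced order. The standard error is √1.5 = 1.22 times as large.
- With the table's order, retest order is determined by group, so it cannot be separated from an interaction of app orientation with first mannequin orientation.

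**Precision.** With equal variances, the standard error of a paired contrast in 40 students relative to a 20 v 20 comparison is √([2(1 − ρ)/40]/[2/20]) = √((1 − ρ)/2). This is 0.59, 0.50 and 0.39 at assumed correlations of 0.3, 0.5 and 0.7. The two comparisons have different estimands, so the ratio shows that the within-student question can be answered with good precision. It does not measure what the A-D comparison loses.

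**The case against.** The Phase one table labels the app stage as teaching and both mannequin stages as testing. If method in Question 3 means app-teaching orientation, A+C v B+D is a randomised comparison at one week and answers it, diluted or not. Statistical Methods also never says that the A-D comparison is made at one week or is meant to settle Question 3. And for Hypothesis 2, testing both positions before the week is not a flaw: it supplies the baseline that each skill's retention needs.

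All of this stands, and it limits the point. A reader might infer that the trial can say nothing about which method is retained better, or that a null one-week result is to be expected. The documents do not support either. The app contrast can be estimated, and they give no figure for how far shared exposure shrinks it. A reader might also extend the problem to Hypothesis 1, that both orientations must be practised. That does not follow: A v D on supine and B v C on upright can be compared in the first mannequin block, before any student has met the other mannequin position. Nor do the documents say that both pre-week blocks fall on the same day, only that both precede the week.

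The objection does not supply a single-orientation group at the retest or a stated retention contrast. The mixed-design ANOVA for the rating scale and checklist might have been meant to carry mannequin position within student, but its factors are not named, and the only within-subject factor the plan names is repetitions.

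**Conclusion.** The point holds in limited form. No group reaches the retest with single-orientation experience. The one-week A-D comparison therefore estimates effects of initial app orientation and first mannequin orientation given exposure to both, and not retention after training in one orientation only. Dilution is likely, on the assumption that repeated mannequin attempts train; its amount is unknown. Hypothesis 2 can be tested on data the trial already collects, but the written analysis does not test it. With the table's retest order, a simple within-student contrast would be off by half of any order effect, assuming 10 students per group.

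**What to change.** In Statistical Methods, answer Question 3 and Hypothesis 2 with a mixed model in all students. The contrast is each student's change from the pre-week session to one week in the upright position against the same student's change in the supine position. Include pre-week order, retest order and Phase two practice assignment, and name the attempts that form the baseline and the retest value.

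Reconcile the fixed retest order in the Phase one table with the random order in Phase two, and use the random or a balanced order so that mannequin position is not confounded with retest order. State the orientation in which the practice group uses the app during the week.

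Add a sentence saying that the one-week A-D comparison estimates the effect of initial app and first mannequin orientation given exposure to both positions, and does not estimate single-orientation retention.

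The cost is slightly more analysis work and a narrower conclusion, with no new students or measurements. Shortening the second-position block before the week to create near-single-orientation groups is not advised: it would weaken the baseline for this contrast and give up transfer data that bear on Question 2.
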